8.3.2 Special Assays or Procedures

DHA analyte

Blood Samples for IV artesunate/DHA will be collected in fluoride-oxalate tubes. Blood samples will be delivered within 15 min of collection to the Infectious Diseases Research Collaboration laboratory in Tororo Hospital for plasma separation. Aliquots of plasma will be stored at -80°C. Plasma aliquots will be shipped intermittently to the IDI Core Laboratory for storage prior to quantification. Aliquots will be tested at either at the IDI Core Laboratory or at the Clinical Pharmacology Analytical Laboratory at JHU, Baltimore, Maryland, USA.

Dried blood spot for known K13 artemisinin resistance mutations

A dried blood spot will be obtained at enrollment for assessment of known K13 artemisinin resistance mutations. Specimens will be shipped to the University of Maryland, Baltimore (UMB) for parasite deoxyribonucleic acid (DNA) extraction and sequencing. The presence of K13 mutations known to be associated with artemisinin resistance will be determined for each specimen.

RNA preservation for parasite variant surface antigen expression analysis

Venous blood will be collected in PAXgene tubes at screening for future analysis of preserved parasite RNA. RNA will be analyzed to determine the predominant variant surface antigens expressed by malaria parasites, allowing for classification of severe malaria cases in this regard.

Other special procedures including neurodevelopmental assessments and BCS will be included in the study MOP and/or SOPs.

8.3.3 Specimen Preparation, Handling, and Shipping

Samples for DHA will be processed using solid-phase extraction and DHA will be quantified by LC MS/MS with an assay validated according to FDA guidelines.

8.3.3.1 Instructions for Specimen Preparation, Handling, and Storage

Detailed SOPs are maintained for these activities. Briefly, blood samples are obtained and processed in the sample processing laboratory according to SOPs. Plasma is frozen in freezers according to SOPs. Dried blood spot specimens will be shipped to the UMB. Frozen samples will be transported to the IDI Translation lab at the IDI in Kampala, and stored there in temperature-monitored freezers or shipped to the DMID clinical material services (DMID-CMS). International Air Transport Association (IATA) guidelines will be followed for specimen handling, transport and shipping.

8.3.3.2 Specimen Shipment

The Investigators will maintain detailed SOPs for specimen transport and storage. All staff and investigators will be trained in the SOPs relevant to their duties and will sign copies of the SOPs to document this training. Copies of SOPs will be available for inspection and review by DMID and study monitors. During the study, SOPs may be modified to improve them, and new SOPs may be developed as needed to improve operations and ensure adherence with the protocol.

9 ASSESSMENT OF SAFETY

9.1 Specification of Safety Parameters

No safety outcome measures are planned for this trial.

9.2 Methods and Timing for Assessing, Recording, and Analyzing Safety Parameters

9.2.1 Adverse Events

An AE includes any noxious, pathological or unintended change in anatomical, physiological or metabolic functions as indicated by physical signs, symptoms and/or laboratory-detected changes occurring in any phase of the clinical study whether associated with the study product and whether or not considered related to the intervention. This definition includes an exacerbation of pre-existing conditions or events, intercurrent illnesses, or drug interaction. Anticipated day-to-day fluctuations of pre-existing conditions that do not represent a clinically significant exacerbation need not be considered AEs. Discrete exacerbations of chronic conditions that are deemed to be different than regularly sustained day-to-day fluctuations, occurring during a study period will be reported as AEs in order to assess changes in frequency or severity.

AEs will be documented in terms of a medical diagnosis. When this is not possible, the AE will be documented in terms of signs and/or symptoms observed by the investigator or reported by the subject at each study visit. Abnormalities in clinical findings and in clinical laboratory testing will only be captured as AEs after the baseline visit. Pre-existing conditions or signs and/or symptoms (including any which are not recognized at study entry but are recognized during the study period) present in a participant before the start of the study will be recorded on the participant's CRF and will be recorded as an AE if deterioration or exacerbation in the condition occurs during the study. Any inpatient overnight hospitalization other than the inpatient stay for severe malaria treatment will be considered an SAE. Information to be collected include event description, date of onset, clinician's assessment of severity, relationship to study product (assessed only by those with the training and authority to make a diagnosis), relationship to study procedures and date of resolution/stabilization of the event. All AEs will be followed to adequate resolution or stabilization.

All AEs must be graded for severity.

FDA defines AE as any untoward medical occurrence associated with the use of a drug in humans, whether or not considered drug related.

Severity of Event: All AEs will be assessed by the PI or appropriate sub-investigator using the Division of AIDS (DAIDS) Table for Grading of Severity of Adults and Pediatric Adverse Events. For unsolicited events not included in the DAIDS Table, the following guidelines will be used to quantify intensity:

- **Mild (Grade 1)-** events require minimal or no treatment and do not interfere with the participant's daily activities.
- **Moderate (Grade 2)-** events result in a low level of inconvenience or concern with the therapeutic measures. Moderate events may cause some interference with functioning and daily activities.
- **Severe (Grade 3)-** events interrupt a participant's usual daily activity and may require systemic drug therapy or other treatment. Severe events are usually incapacitating.

If an AE changes in severity, it is not a new event, and each AE is documented at its highest severity grading. AEs characterized as intermittent require documentation of onset and duration of each episode.

9.2.2 Serious Adverse Events

An AE or suspected adverse reaction is considered “serious” if, in the view of either the investigator or sponsor, it results in any of the following outcomes:

- Death,
- A life-threatening AE*,
- Inpatient hospitalization or prolongation of existing hospitalization,
- A persistent or significant incapacity or substantial disruption of the ability to conduct normal life functions, or
- A congenital anomaly/birth defect.
- Important medical events that may not result in death, be life-threatening, or require hospitalizations may be considered serious when, based upon appropriate medical judgment they may jeopardize the patient or subject and may require medical or surgical intervention to prevent one of the outcomes listed in this definition. Examples of such medical events include allergic bronchospasm requiring intensive treatment in an emergency room or at home, blood dyscrasias or convulsions that do not result in inpatient hospitalization, or the development of drug dependency or drug abuse.

* Life-threatening AE. An AE is considered “life-threatening” if, in the view of either the investigator or sponsor, its occurrence places the patient or subject at immediate risk of death. It does not include an AE, had it occurred in a more severe form, might have caused death.

All SAEs will be:

- recorded on the appropriate SAE form and electronic case report form (eCRF)
- reviewed and evaluated by an ISM, DMID, and the IRB, if indicated

9.3 Reporting Procedures

AEs and SAEs will be documented from the first study intervention, through the end of the follow-up period.

All AEs and SAEs will be captured on the appropriate data collection form. Information to be collected includes event description, date of onset, investigator assessment of severity, relationship to study product, date of resolution of the event, and outcome.

9.3.1 Serious Adverse Events

AEs will be followed to adequate resolution or stabilization for participants enrolled in the study. After termination of the study, participants will be referred to appropriate care for follow-up of ongoing AEs. Any AE that is associated with the study drug will be followed to resolution or stabilization with the expectation that it will remain chronic. Any AE that meets a protocol-defined serious criterion must be submitted to DMID within 24 hours of site awareness via the IDES or a DMID SAE form. SAE information is reported via the Adverse Event eCRF in Advantage eClinical. At the time of submission of the AE eCRF in Advantage eClinical, an automatic email will be sent to the DMID Medical Monitor, DMID, and the study PI, alerting them to the occurrence of an SAE. No further steps are necessary to notify the DMID Medical Monitor. Updates to the SAE should be reported via the AE eCRF.

In addition to the reporting to DMID, the investigator must also report to the ethics committee and IRB. Any AE that meets a protocol-defined serious criterion and is considered related to the investigational product must be submitted, unless otherwise requested by the ISM, sponsor or the investigators:

- Within 48 hours to the Uganda IRB
- Within 5 days to the University of Maryland IRB

For other AEs that meet a protocol-defined serious criterion and are considered not related to the investigational product, this information can be submitted, unless otherwise requested by the ISM, sponsor or the investigators:

- In the annual summary to the Uganda IRB
- In the annual summary to the University of Maryland IRB

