2.3 Potential Risks and Benefits

2.3.1 Potential Risks

No significant additional risks are anticipated as participants will be receiving standard of care antimalarial therapy per national guidelines. Frequent blood draws are also common for patients with severe malaria. The amount of blood drawn for research purposes will be minimized to reduce added risk.

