9.5 Halting Rules

Decisions to halt or pause the study will be made by the host REC and DMID.

Subsequent review of serious, unexpected, and related AEs by the Medical Monitor, ethics review committee, the sponsor, or relevant local regulatory authorities may also result in suspension of further trial interventions/administration of study product at a site. The host REC and study sponsor retain authority to suspend additional enrollment and study interventions/administration of study product for the entire study, as applicable.

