14.3 Safety Data

14.3.1 Displays of Adverse Events

Table 29: Overall Summary of Adverse Events

	All Participants (N = xx)	
Participants ^a with	n	%
At least one unsolicited adverse event	x	x
At least one related unsolicited adverse event	x	x
Mild (Grade 1)	x	x
Moderate (Grade 2)	x	x
Severe (Grade 3)	x	x
Not yet assessed	x	x
At least one severe (Grade 3) unsolicited adverse event	x	x
Related	x	x
Related to IV artesunate	x	x
Related to oral ACT	x	x
Related to study procedures	x	x
Unrelated	x	x
At least one serious adverse event ^b	x	x
At least one related, serious adverse event	x	x
At least one serious adverse event related to IV artesunate	x	x
At least one serious adverse event related to oral ACT	x	x
At least one serious adverse event related to study procedures	x	x
At least one adverse event leading to early termination ^c	x	x

N = Number of participants in the Safety Population
^a Participants are counted once for each category regardless of the number of events.
^b A listing of Serious Adverse Events is included in [Table 31](#).
^c As reported on the Adverse Event eCRF.

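### The dated SAE reports to the two IRBs are triggered only by relatedness to the investigational product, so an SAE caused by a study procedure defaults to the annual summary

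*Protocol*

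**What the plan says.** Protocol section 9.3.1 divides the investigator's SAE reports to ethics bodies into two groups. The first is expedited: "Any AE that meets a protocol-defined serious criterion and is considered related to the investigational product must be submitted", with the deadlines "Within 48 hours to the Uganda IRB" and "Within 5 days to the University of Maryland IRB". The second covers the rest: "For other AEs that meet a protocol-defined serious criterion and are considered not related to the investigational product, this information can be submitted", in the annual summary to both IRBs. Each sentence carries the same exception, which lets the ISM, the sponsor or the investigators ask for something different. The same section sends every SAE to DMID within 24 hours of site awareness, whatever its cause.

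Elsewhere the documents treat study procedures as a separate cause of harm. Section 9.2.1 includes in the AE record "relationship to study procedures and date of resolution/stabilization of the event". SAP Table 29 has its own row for participants with "At least one serious adverse event related to study procedures". Section 9.3, however, lists only relationship to study product among the items collected.

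On risk, section 2.3.1 states: "No significant additional risks are anticipated as participants will be receiving standard of care antimalarial therapy per national guidelines". The physical risk to participants that it then itemises, in 2.3.1.1, is blood drawing (bleeding, haematoma, infection). On authority to stop, section 9.5 says: "Decisions to halt or pause the study will be made by the host REC and DMID".

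**The concern.** The drug is standard of care, and the protocol says it adds no significant risk. The physical risk that the protocol attributes to taking part is the blood sampling. The expedited rule is therefore built around the standard-of-care drug and leaves out the procedures. A serious event attributed to a research procedure alone is placed by default on the slowest route to the committees that judge whether those procedures are acceptable in severely ill children. One of those committees, the host REC, shares the halting decision. Section 9.5 also foresees ethics-committee review of serious, unexpected and related events, and does not restrict relatedness there to the product. Section 9.3.1 guarantees dated notice only of the product-related ones.

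**Working it through.** This is a comparison of texts; the plan gives no figure to reproduce. Take an SAE judged related to a study procedure and not to artesunate, and follow each route by which it could reach an ethics body or the sponsor.

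| Route | Recipient | Depends on relatedness? | Deadline |
|---|---|---|---|
| Protocol 9.3.1, expedited | Uganda IRB; University of Maryland IRB | Yes, to the investigational product; this SAE does not qualify | 48 hours; 5 days |
| Protocol 9.3.1, remainder | Both IRBs | Applies because the SAE is not product-related | Annual summary, worded permissively |
| Protocol 9.3.1, exception | As requested | No | None; acts only if someone asks |
| Protocol 9.3.1, sponsor report | DMID | No | 24 hours |
| Protocol 9.6 (repeated in SAP 6.6) | REC and DMID, through the ISM's assessment | No | Protocol says timely, with no number of days; SAP gives no timing |
| Protocol 14.2 | All REC/IRBs and DMID | No | None; applies only where required |
| Protocol 9.2.2 | ISM, DMID and the IRB | No | None; IRB review only if indicated |

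Three results follow.

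1. The only row with a fixed deadline that covers this SAE is the 24-hour report to DMID, which is not an IRB.
2. The host REC should hear of the event through the ISM, but with no stated time limit. Section 9.6 also assumes that the REC is itself notified of the SAE, which fits poorly with an annual default in section 9.3.1.
3. The University of Maryland IRB is not named in the ISM route. Apart from the annual summary or a request, it depends on the conditional wording of sections 14.2 and 9.2.2.

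*Size of the delay.* The documents give no date for the annual summary. An event just before it would wait hardly at all; an event just after the previous one would wait about 12 months. The range is therefore roughly 0 to 12 months, against 48 hours or 5 days. The Protocol Summary plans 6 months of enrolment, and section 4 puts the whole trial at about 12 months. A first annual summary at 12 months would come about 12 − 6 = 6 months after planned enrolment closed. SAP section 5 reports that only 46 participants had been enrolled by the end of the planned period, so actual enrolment may have run longer and this comparison applies to the plan.

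*Scope of the term.* Protocol section 6.1 and SAP section 4.4.2 describe only artesunate for injection, with its diluents, as the product. Study procedures are outside the term on any reading. Oral ACT is less clear: section 9.3.1 does not define the term, SAP section 9.3.2 and Table 29 attribute events to oral ACT separately from IV artesunate, and SAP Table 31 groups both under study treatment.

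**The case against.** The best defence is that section 9.3.1 is one layer among several. The annual route is a permissive default, and three parties can displace it. DMID, which shares the halting decision, knows of every SAE within a day and can ask for faster submission. The ISM reports to the REC with no relatedness filter, so the committee with halting authority should be reached. Section 14.2 covers serious events to all REC/IRBs, including the University of Maryland, and what it requires may be fixed by IRB policies that are not in these documents.

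Most of this stands. It rules out a stronger reading that a reader might take from section 9.3.1 alone, namely that a procedure-related SAE simply goes into the annual summary and reaches no committee before then. The documents do not say that. What the defence does not supply is a dated duty. The exception depends on someone using it, and it qualifies the expedited rule as well as the annual one. The ISM route has no number of days and omits one of the two IRBs. Sections 14.2 and 9.2.2 are conditional.

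It can also be said that oral ACT is national-guideline care and so not a risk added by the research. That is fair. For oral ACT the protocol needs a clear statement; its omission from the trigger is not established as an error.

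**Conclusion.** The point holds for study procedures. The investigator's 48-hour and 5-day reports depend on relatedness to the investigational product, and an SAE due to a procedure alone defaults to the annual summary unless someone requests otherwise. The trigger is narrower than the causality categories that the study already records and tabulates. For oral ACT the text is ambiguous.

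The size is modest: one missing category in a reporting rule, with a possible delay of up to about 12 months and partial cover from DMID and the ISM. This assumes that the Uganda IRB of section 9.3.1 is the host REC of sections 9.5 and 9.6, and that investigational product means artesunate for injection.

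A reader might add up the blood volumes in section 8.1 (8.25 + 11.5 + 3.5 + 3 × 3.25 + 3 + 3 = 39.0 mL through Day 7) and infer that each child has that much drawn. The documents do not support this. It is an upper bound for a child with every scheduled draw. Section 7.3 drops the remaining daily visits after early discharge, section 7.1 lets recent results serve as both screening and baseline, and section 2.3.1 notes that frequent draws are common in severe malaria anyway.

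Nothing here affects the sample size, power, error rate or any planned analysis.

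**What to change.** In Protocol section 9.3.1, make the expedited trigger 'related to the investigational product or to any study procedure', and limit the annual-summary sentence to SAEs 'not related to either'. State in the same place whether oral ACT counts as investigational product for this rule. Add relationship to study procedures to the items listed in section 9.3, so that it matches section 9.2.1. Reconcile the timing in section 9.3.1 with sections 9.6 and 14.2, including when the REC hears of an SAE and how the University of Maryland IRB does.

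The cost is a short protocol amendment, which section 14.2 puts through the local REC, the University of Maryland IRB and DMID. The causality categories are already in the planned SAP tables, so no new output is needed. The downside is at most a few more expedited IRB reports; section 15.3 itself expects few SAEs.

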9.4 Type and Duration of Follow-up of Subjects after Adverse Events

Investigators will follow up subjects with AEs and SAEs until the event has resolved, or, if a chronic condition has developed, until the end of the study follow-up period. Outcome will be assessed as Recovered/Resolved, Recovered/Resolved with Sequelae, Recovering/Resolving, Not recovered/Not resolved, or Fatal.

9.5 Halting Rules

Decisions to halt or pause the study will be made by the host REC and DMID.

Subsequent review of serious, unexpected, and related AEs by the Medical Monitor, ethics review committee, the sponsor, or relevant local regulatory authorities may also result in suspension of further trial interventions/administration of study product at a site. The host REC and study sponsor retain authority to suspend additional enrollment and study interventions/administration of study product for the entire study, as applicable.

9.6 Safety Oversight (ISM)

A Safety Monitoring Committee is not required for this protocol.

An ISM is a physician with relevant expertise whose primary responsibility is to provide to DMID an independent safety assessment in a timely fashion. Participation is for the duration of the DMID study and is a voluntary position that does not receive payment.

The ISM:

- Is near the study site and has the authority and ability to readily access study participant records in real time.
- May be a member of the participating institution's staff but preferably be from a different organizational group within the institution.
- Should not be in a direct supervisory relationship with the investigator.
- Should have no direct involvement in the conduct of the study.

The ISM will:

- Sign a Conflict of Interest (COI) certification at the time they are asked to participate and provide updates to this information as needed.
- Receive reports of SAEs from the site investigator and will be notified by email when the REC and DMID are notified of the SAE.
- Evaluate the SAE and report their clinical assessment to the REC and DMID, through DMID-Clinical Research Operations and Management Support (CROMS) Safety Oversight Committee Support (SOCS) in a timely manner and email the report to REC and DMID-CROMS SOCS.
- Communicate with the investigator at the participating site as needed.
- Review additional safety related events at the request of the REC and DMID.
- Provide additional information to REC and DMID by teleconference as requested.

10 CLINICAL MONITORING

10.1 Site Monitoring Plan

Study site monitoring will be conducted by the internal IDI monitor and DMID clinical monitoring contractor to ensure that the conduct of the trial is in compliance with the currently approved protocol, amendment(s), ICH, sponsor requirements GCP standards, and regulatory guidelines are being followed. Clinical monitoring will also verify that any critical study procedures are completed following specific instructions in the protocol-specified MOP. A pre-trial monitoring visit will be made to the study site, including the clinical laboratory. All records will be made available to monitors, including regulatory files, CRFs and source documents, quality assurance (QA)/quality control (QC) documentation, SOPs, etc. Additional study site visits may be made during the trial and at the end of the surveillance period.

In addition, monitors from the University of Maryland may make study site visits, in coordination with the primary monitoring group designated by DMID.

In conjunction with the clinical monitoring contractor designated by the sponsor, a detailed monitoring plan will be developed. This document describes who will conduct the monitoring, at what frequency monitoring will be done, and what level of detail monitoring will be conducted. The clinical monitoring plan will be written by DMID and the DMID clinical monitoring contractor. This separate monitoring plan will be agreed upon with the Office of Clinical Research Affairs (OCRA) and will describe protocol-specific items to be monitored. The monitoring plan will include the number of participant charts to be reviewed, which/what proportion of data fields and what will be monitored, who will be responsible for conducting the monitoring visits, and who will be responsible for ensuring that monitoring findings are addressed. Monitoring visits will include, but are not limited to, review of regulatory files, accountability records, electronic case report forms (eCRFs), ICFs, medical and laboratory reports, site study intervention storage records, training records, and protocol and GCP compliance. Site monitors will have access to each participating site, study staff and all study documentation according to the DMID-approved CMP. Study monitors will meet with all participating site PIs to discuss any problems and outstanding issues and will document site visit findings and discussions.

